**Table 2: Modified IWG 2003 AML Response Criteria**

Response a	ASTX727-02 Specific Criteria
CR	ANC $\geq$ 1000/ $\mu$ L, Platelets $\geq$ 100,000/ $\mu$ L, independence from RBC and platelet transfusions over the past week, no leukemic blasts b <5% leukemic blasts
CRi	All CR criteria except ANC <1000/ $\mu$ L or Platelets <100,000/ $\mu$ L
CRp	All CR criteria except Platelets <100,000/ $\mu$ L and platelet transfusions over the past week
PR	All CR criteria except decrease of $\geq$ 50% in leukemic blasts to level of 5% to 25%

ANC=absolute neutrophil count; CR=complete response; CRp=complete response with incomplete platelet recovery; CRi=CR with incomplete blood count recovery; PR=partial response.

a Responses are based on both PB and BM conditions.

b For the purpose of response assessment and according to published IWG criteria, blasts may be seen in PB as rare PB blasts may be identified during regeneration, but the subject is in CR if BM blasts are <5% with no Auer rods.

Source: [Cheson et al 2003](#); [Kantarjian et al 2012](#)

For subjects who experience different response levels at different visits, the best response (see [Table 2](#)) will be used for summary and analyses. Overall objective response will be the number of subjects achieving CR, CRi, and PR with each subject counted once according to their best response. CRp, a subcategory of CRi will be listed under CRi. Composite response rates, CR + CRi (either CR or CRi), CR + CRi + PR (either CR or CRi or PR), CR + CRh (either CR or CRh) and CRh, will also be included in the response analysis.

Subjects with these different response categories will be listed and summarized using frequency counts and proportion of subjects with each category. The 95% Clopper-Pearson confidence interval will be provided for each response rate. Subgroup analyses such as by age category ( $<75$ ,  $\geq 75$ ) may be performed.

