CR with incomplete platelet recovery (CRp)			
 
• CRp is not defined in IWG 2003 or ELN 2017; CRp was first defined by Sievers et al 2001 (as referenced in IWG 2003) as follows: CR except no platelet count recovery requirement (but meeting ANC requirement: ANC <math>\geq 1.0 \times 10^9/L</math> (1000/<math>\mu</math>L))
 
• CRp is a subset of CRi (ie, overlaps, thus should not be additive in a composite response rate)
 
• All CR criteria (including ANC criterion) except for residual thrombocytopenia (platelet <math><100 \times 10^9/L</math> [100,000/<math>\mu</math>L])
 
• Example: ANC 1,200/<math>\mu</math>L and platelet 80,000/<math>\mu</math>L
 
	
 
• The protocol defines as a parallel assessment along with CRi, CRp is “ANC <math>\geq 1000/\mu</math>L, Platelets <math><100,000/\mu</math>L, independence from RBC transfusions over the past week, no leukemic blasts”
 
• In the protocol, CRi is modified and defined as the non-CRp subtype of the original CRi IWG 2003 so subjects are not counted twice (Kantarjian et al, 2012)
 
 
RECOMMENDATIONS: -Approach like DAGO-016, which reports CRp as a subset of CRi in final data table summary. Note that in Kantarjian et al, 2012 paper, the table is presented incorrectly. -CR+CRp composite are additive for an overall rate (Kantarjian et al, 2012 and Sievers et al, 2001)

AML Response Assessment	IWG 2003 AML Response Criteria 	ELN 2017 AML Response Criteria 	Issues Requiring Clarification(s)	Study-specific Modification(s): ASTX727-02

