**APPENDIX C: PROGRAMMING GUIDELINES**

Table of response AML assessment status and programmable measures in ASTX727-02 study

Response Assessment Status	Programmable Measures*	Data not evaluable or not easy to capture in EDC (defer to hematopathologist and clinical investigator assessment; or sponsor medical adjudication)
CR	
 
• Marrow blasts: <5%
 
• ANC: <math>\geq 1000/\mu\text{L}</math>
 
• Platelets: <math>\geq 100,000/\mu\text{L}</math>
 
• No RBC and/or platelet transfusion within 7 days of BM evaluation
 
• Peripheral blasts <math>\leq 1\%^1</math>
 
	
 
• Auer rods
 
• Extramedullary disease
 
• Minimum 100 nucleated cell count from aspirate
 
• Flow data evaluating blast morphology
 
• Peripheral blasts present at low % (could be due to regeneration)
 
• CR criteria met but transfusion within 7 days of BM evaluation due to a medical situation
 
• Medical adjudication required when BM and CBC data not assessed on the same day
 

CRi  assess independently in all non-CR cases except progressive disease or relapse/recurrence	
 
• Marrow blasts: <5%
 
• ANC: <math>\geq 1000/\mu\text{L}</math> OR Platelets: <math>\geq 100,000/\mu\text{L}</math>
 
• Transfusion: no RBC and/or platelet transfusion within 7 days of BM evaluation
 
• Peripheral blasts <math>\leq 1\%^1</math>
 
	
 
• Auer rods
 
• Extramedullary disease
 
• Minimum 100 nucleated cell count from aspirate
 
• Flow data evaluating blast morphology
 
• Peripheral blasts present at low % (could be due to regeneration)
 
• CRi criteria met but transfusion within 7 days of BM evaluation due to a medical situation
 
• Medical adjudication required when BM and CBC data not assessed on the same day
 

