CRp  assess independently in all non-CR cases except progressive disease or relapse/recurrence	
 
• Marrow blasts: <5%
 
• ANC: <math>\geq 1000/\mu\text{L}</math>
 
• Platelets: any platelet count <100
 
• Transfusion: no RBC transfusions within 7 days of BM evaluation (no platelet recovery needed so this is independent of platelet transfusion status)
 
• Peripheral blasts <math>\leq 1\%^1</math>
 
	
 
• Auer rods
 
• Extramedullary disease
 
• Minimum 100 nucleated cell count from aspirate
 
• Flow data evaluating blast morphology
 
• Peripheral blasts present at low % (could be due to regeneration)
 
• CRp criteria met but transfusion within 7 days of BM evaluation due to a medical situation
 
• Medical adjudication required when BM and CBC data not assessed on the same day
 

CRh	
 
• Marrow blasts: <5%
 
	
 
• Auer rods
 

Response Assessment Status	Programmable Measures*	Data not evaluable or not easy to capture in EDC (defer to hematopathologist and clinical investigator assessment; or sponsor medical adjudication)
assess independently in all non-CR cases except progressive disease or relapse/recurrence	
 
• ANC: <math>\geq 500/\mu\text{L}</math>
 
• Platelets: <math>\geq 50,000/\mu\text{L}</math>
 
• Transfusion: no RBC and/or platelet transfusions within 7 days of BM evaluation
 
• Peripheral blasts <math>\leq 1\%^1</math>
 
	
 
• Extramedullary disease
 
• Minimum 100 nucleated cell count from aspirate
 
• Flow data evaluating blast morphology
 
• Peripheral blasts present at low % (could be due to regeneration)
 
• CRp criteria met but transfusion within 7 days of BM evaluation due to a medical situation
 
• Medical adjudication required when BM and CBC data not assessed on the same day
 

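### The SAP declares CRp a subset of CRi, but its CRi criteria keep a no-platelet-transfusion condition that CRp waives, so a platelet-transfused CRp subject fails CRi as written

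*SAP*

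**What the plan says.** - **Subset rule.** After defining overall objective response as CR, CRi and PR, SAP Section 7.5.1 adds that "CRp, a subcategory of CRi will be listed under CRi". The CRp row of the response table in SAP Appendix 1 says "CRp is a subset of CRi (ie, overlaps, thus should not be additive in a composite response rate", and its recommendation is to report CRp as a subset of CRi.
- **CRi criteria.** The CR row of Table 2 requires "independence from RBC and platelet transfusions over the past week". CRi is every CR condition other than the ANC or platelet count, so the transfusion condition carries over. Appendix C says so directly in its CRi row: "Transfusion: no RBC and/or platelet transfusion within 7 days of BM evaluation".
- **CRp criteria.** Table 2 lifts both the platelet count and the platelet-transfusion condition. Appendix C explains: "no platelet recovery needed so this is independent of platelet transfusion status".
- **Derivation.** Appendix C tells programmers to assess CRi, CRp and CRh separately: "assess independently in all non-CR cases except progressive disease or relapse/recurrence". Section 7.5.1 gives the evaluation of response to the sponsor's medical monitors, assisted by programmed listings.
- **Non-responders.** Section 7.5.1 classes anyone who is not CR, CRi, PR or not evaluable as a non-responder. The corresponding row of Appendix C also requires the absence of CRp and CRh. Section 7.5.2 counts CRp and CRh as responses, in the same tier as CRi.

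The protocol supplied covers MDS and CMML only and does not define these AML categories, so it cannot settle the matter.

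**The concern.** A category with a looser transfusion condition cannot be a subset of one with a stricter condition. CRp enters overall objective response and the CRi composites only through its claimed membership of CRi, because Section 7.5.1 names only CR, CRi and PR. If the CRi criteria are coded as written, a platelet-transfused CRp subject drops out of all of these. Under the non-responder sentence of Section 7.5.1 taken alone, that subject becomes a non-responder, while Section 7.5.2 assigns the same subject a time to response.

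Two related definitions carry the same risk:

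- **CRh cut-offs.** Section 7.5.1 uses strict inequalities (ANC above 500/µL, platelets above 50,000/µL). The CRh rows of Appendix 1 and Appendix C use inclusive ones.
- **Both counts low.** Table 2 defines CRi by low ANC *or* low platelets, which read inclusively admits subjects with both low. The CRi rows of Appendix 1 and Appendix C require the other count to meet the CR threshold.

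**Working it through.** The documents state no response rate for this study, so there is no planned figure to reproduce. The check is a classification, followed by simple arithmetic for size.

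**1. Enumerating the criteria.** Take marrow blasts below 5% and peripheral blasts at most 1%. Cross ANC (400, 800, 1200/µL) with platelets (40, 80, 120 × 10⁹/L), RBC transfusion (yes/no) and platelet transfusion (yes/no). That gives 3 × 3 × 2 × 2 = 36 profiles. The rules applied were:

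- CR: ANC ≥1000, platelets ≥100, no RBC or platelet transfusion.
- CRi (Table 2, inclusive reading): ANC <1000 or platelets <100, no RBC or platelet transfusion.
- CRi (Appendix C): not CR; ANC ≥1000 or platelets ≥100; no RBC or platelet transfusion.
- CRp: ANC ≥1000, platelets <100, no RBC transfusion.
- CRh (Appendix C): not CR; ANC ≥500 and platelets ≥50; no RBC or platelet transfusion.

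**2. CRp against CRi.** Four profiles meet CRp:

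| ANC | Platelets | Platelet transfusion | CRp | CRi, Table 2 | CRi, Appendix C | CRh |
|---|---|---|---|---|---|---|
| 1200 | 40 | no | yes | yes | yes | no |
| 1200 | 80 | no | yes | yes | yes | yes |
| 1200 | 40 | yes | yes | no | no | no |
| 1200 | 80 | yes | yes | no | no | no |

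The two transfused profiles fail CRi under either version. They also fail CR, and they fail PR because marrow blasts are below 5%. The subset relation therefore fails for exactly the subjects whom the CRp waiver admits.

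**3. Both counts low.** Four untransfused profiles (ANC 400 or 800 with platelets 40 or 80) are CRi under the inclusive reading of Table 2 and not CRi under Appendix C. Of these, only ANC 800 with platelets 80 is CRh. The same holds for ANC 700 with platelets 70: CRi on one reading, CRh only on the other. On the second reading that subject is a non-responder in Section 7.5.1 and a responder in Section 7.5.2.

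**4. Size per subject.** SAP Section 4.0 plans about 85 randomized. The Efficacy Analysis Set is the treated subjects, so the denominator may be slightly smaller.

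- N = 85: 100/85 = 1.18 points per subject.
- N = 80 (an assumption): 100/80 = 1.25 points.
- Assumed range of 1 to 5 subjects at N = 85: 1.2 to 5.9 points.

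**5. Illustration.** Assume 20 of 85 with CR+CRi under the literal criteria, and let k be the number of platelet-transfused CRp subjects added by the subset rule. The Clopper-Pearson 95% limits are the 0.025 quantile of Beta(x, n−x+1) and the 0.975 quantile of Beta(x+1, n−x).

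| k | x/n | Rate | 95% CI |
|---|---|---|---|
| 0 | 20/85 | 23.5% | 15.0 to 34.0 |
| 1 | 21/85 | 24.7% | 16.0 to 35.3 |
| 3 | 23/85 | 27.1% | 18.0 to 37.8 |
| 5 | 25/85 | 29.4% | 20.0 to 40.3 |

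**6. CRh cut-offs.** The strict and inclusive versions differ only for a value recorded exactly at ANC 500/µL or platelets 50,000/µL. The rounding footnote to Appendix C itself warns that an ANC reported at that threshold affects the classification.

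**The case against.** The strongest reply is that the plan already answers the counting question. Section 7.5.1 puts CRp under CRi immediately before it lists the composites. Appendix 1 recommends that presentation, Section 7.5.2 ranks the two in one tier, and the summary of changes gives the subset relation as the reason. This largely stands. A reader might infer that the response rates are left open, to be decided by whichever section a programmer follows. The documents do not support that: the intention is fairly clear, and the defect is a CRi transfusion condition that contradicts it.

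The instruction to assess the subtypes independently also proves less than it seems to. Appendix 1 explains that they overlap, and checking each separately fits with nesting them in the table afterwards.

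Medical adjudication helps only in part. The CRi row of Appendix C refers to the monitors the case "CRi criteria met but transfusion within 7 days of BM evaluation due to a medical situation". Appendix D item 3 reviews the circumstances of any transfusion within a week, expects such cases to be rare, and has elective transfusion in view. It gives no rule for an ordinary platelet transfusion given for the persisting thrombocytopenia that CRp allows.

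Two other inferences are tempting but should not be pressed.

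- **CR+CRp exceeding CR+CRi.** Appendix 1 says "CR+CRp composite are additive for an overall rate", and the sample shell in Appendix E has a CR+CRp row, so literal coding could produce a result impossible for a subset. But Section 7.5.1 does not name CR+CRp among its composites, and the result disappears once CRp is counted in CRi.
- **Stable and progressive disease.** Appendix 1 still says these are not assessed, and the shell has no non-responder row, which might suggest subjects without a category. Section 7.5.1 now defines both, the non-responder rules in Section 7.5.1 and Appendix C largely cover the remainder, and the shell is only a sample. This is housekeeping.

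**Conclusion.** The point holds as an internal contradiction in the response definitions and is minor. Literal use of the CRi criteria would make the four affected summaries too low relative to the plan's own subset rule. The per-subject size rests on the planned 85. The number of such subjects is not given, and the 20/85 base and the range of 1 to 5 are assumptions. For scale, the interval at 20/85 is 34.0 − 15.0 = 19.0 points wide, so a single subject matters little to interpretation.

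The both-counts-low conflict is substantive rather than editorial, because it moves subjects between CRi and CRh-only or no CR subtype. It too is worth about 1.2 points per subject at N=85, with an unknown count. The CRh cut-off conflict reaches CRh, CR+CRh and the duration of combined CR and CRh, only for values at the threshold.

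Section 7.5 makes efficacy descriptive, with no formal comparison between sequences, so no error rate or test is involved.

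**What to change.** 1. Reconcile the CRi transfusion condition in Table 2 and Appendix C with the subset rule. The simplest way is one derivation sentence: every CRp counts as CRi in the CRi row, the CRi composites and overall objective response, and is not a non-responder under Section 7.5.1.
2. Choose one set of CRh inequalities and use it in Section 7.5.1, Appendix 1 and Appendix C.
3. State whether CRi requires exactly one low count or allows both, and use that in Table 2, Appendix 1 and Appendix C. Then give one non-responder definition that agrees with Section 7.5.2 on CRh-only subjects.
4. As housekeeping, remove the leftover statements that stable and progressive disease are not assessed, and match the shell rows to the categories kept.

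The cost is SAP wording, a few lines of derivation code and at most one or two shell rows. No new data are needed.

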## 7.5.2 Time to First Response and Time to Best Response

Both time to first response and time to best response will be calculated and analyzed for subjects who achieve a response of CR, CRi (or CRp or CRh), or PR. Time to first response is defined as the time, in days, from the date of first treatment (C1D1) to the first date when any response is achieved. Time to best response is similarly defined as the time, in days, from the date of first treatment (C1D1) to the first date when a subject's best response, in the order of CR, CRi (or CRp or CRh), or PR, is achieved. The times to first response and best response will be summarized using mean, standard deviation, median, minimum, and maximum. Time to CR will be summarized similarly.

### 7.5.3 Duration of Response

A combined duration of CR and CRh (in number of days) will be calculated from the first time a CR or CRh is observed to the date of the earliest of the following 3 events: (1) relapse (defined as the earliest time point whereby BM assessment or PB assessment by the investigator indicate relapse/disease progression due to confirmed reappearance of leukemic blasts in PB or  $\geq 5\%$  leukemic blasts in BM, or clinical progression determined by the investigator), (2) start of alternative therapy (except hematopoietic cell transplantation [HCT]) or (3) death. In the absence of any event, the combined duration of CR and CRh will be censored at the last available time point (BM assessment, PB assessment, or safety/long-term follow-up visit) at which an event was not observed. Duration of combined CR and CRh will be analyzed using the Kaplan-Meier method for subjects who achieved a CR or CRh during the study; the median and quartiles of the duration, as well as their respective 95% CIs will be provided. Duration of CR or CRp and duration of CR will be calculated and analyzed similarly.

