#### 11.7.3 Leukemia-Free Survival

The number of days from randomization to the date when bone marrow or peripheral blood blasts reach  $\geq$ 20%, or death from any cause, will be measured for subjects in the Efficacy Analysis Set. Subjects who do not have events in leukemia-free survival will be censored on the last date of bone marrow or peripheral blood blasts assessment, whichever is later. Subjects who have bone marrow or peripheral blood blasts  $\geq$ 20% at baseline will be censored at the date of randomization. Leukemia-free survival will be presented using a Kaplan-Meier estimate. The 95% CI for the median of leukemia-free survival will be provided using the Kaplan-Meier procedure.

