#### 3.2.2 Secondary Endpoints

- Safety as assessed by AEs, concomitant medications, physical examination, clinical laboratory tests (hematology, serum chemistry, and urinalysis), vital signs, Eastern Cooperative Oncology Group (ECOG) performance status, and electrocardiogram (ECG).
- Maximum %LINE-1 demethylation.
- Additional secondary PK parameters.
- Clinical response (complete response [CR], CR with incomplete platelet recovery [CRp], and CR with incomplete blood count recovery [CRi] based on modified IWG 2003 AML response criteria ([Cheson et al 2003](#)) and as in the DACO-016 study (ie, CRp as a subset of CRi) ([Kantarjian et al 2012](#)). In addition, complete response with partial hematologic recovery (CRh) will also be assessed. CRh will be reported as in [Kantarjian et al 2017](#) and as used in [DiNardo et al 2020](#)).
- Time to first response, time to best response, and time to CR.
- Duration of CR and duration of combined CR and CRh, defined respectively as the time interval from the first CR to time of relapse and the time interval from the first CR or CRh to time of relapse.
- Red blood cell (RBC) or platelet transfusion independence (TI).
- Overall survival (OS), defined as the number of days from the date of randomization to the date of death from any cause.
- Survival rates at 6 months, one year, and two years.
- Event-free survival (EFS), defined as the number of days from the date of randomization to the date of treatment failure or death from any cause, whichever occurs first.
- Progression-free survival (PFS), defined as the number of days from the date of randomization to the date disease progression or death from cause, whichever occurs first.

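### SAP 7.5.3 lets duration of response be censored at a follow-up visit that need not include a blast assessment, which can lengthen it; separately, SAP 3.2.2 and 7.5.3 end the duration at different events

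*SAP*

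**What the plan says.** SAP 7.5.3 (Duration of Response) runs the combined duration of CR and CRh from first response "to the date of the earliest of the following 3 events: (1) relapse". That relapse definition covers blasts in blood or marrow, "or clinical progression determined by the investigator". The other two events are listed as "2) start of alternative therapy (except hematopoietic cell transplantation [HCT]) or (3) death". Without an event, the duration is "censored at the last available time point (BM assessment, PB assessment, or safety/long-term follow-up visit) at which an event was not observed". The rule carries over to the other durations: "Duration of CR or CRp and duration of CR will be calculated and analyzed similarly". Results are Kaplan-Meier medians and quartiles with 95% CIs.

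SAP 3.2.2 (Secondary Endpoints) defines duration of CR as "the time interval from the first CR to time of relapse" and the combined duration as "the time interval from the first CR or CRh to time of relapse". It does not mention death or new therapy.

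For leukemia-free survival in MDS/CMML, protocol 11.7.3 ties censoring to disease assessment: event-free subjects "will be censored on the last date of bone marrow or peripheral blood blasts assessment, whichever is later".

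**The concern.** The usual principle is that a subject counts as still in remission only up to the last time somebody checked. Relapse in 7.5.3 rests largely on blast counts, so the absence of an event at a contact without a blood or marrow result may only mean that relapse was not looked for. A responder who stops assessment, relapses unseen and stays in contact continues to contribute remission time until a later event is recorded or follow-up ends. Transplanted responders are one route to this: transplant is neither an event nor a censoring point in 7.5.3, and they may come off the study's assessment schedule.

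The second problem is separate. The same data give different event counts under 3.2.2 and 7.5.3. A death in remission ends the duration under 7.5.3 but is not named as an event in 3.2.2. What is at stake is the reported median of a listed secondary endpoint, across three versions of the duration.

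**Working it through.** **No plan figure to reproduce.** Neither document gives an expected median, event count or precision for duration of response. All numbers below are illustrations on stated assumptions.

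**Step 1: what a follow-up contact may contain.** In the supplied protocol, the 30-day visit (9.5.5) may be by telephone, needs only adverse events as a minimum, and lists no hematology or marrow. The 3-monthly survival contact (9.5.6) may also be by telephone. On treatment, hematology including blast percentage is taken on Days 1 and 15 of Cycle 3 onward (Table 9 notes), so the gap arises mainly after treatment stops. This is the US MDS/CMML protocol. The SAP rests on Amendment 2.6 Europe (SAP 1.0), which is not available here.

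**Step 2: upper end, where only death is captured once assessment stops.** Assumptions: exponential times; true median to relapse 9 months, so λ = ln 2/9 = 0.0770 per month; median survival after relapse 8 months, so δ = ln 2/8 = 0.0866; assessment stops at rate μ per month; contact continues to the cutoff. The 7.5.3 rule then estimates

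S(t) = e^(−λt) + λ[(e^(−λt) − e^(−δt))/(δ − λ) − (e^(−(λ+μ)t) − e^(−δt))/(δ − λ − μ)].

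For μ = 0.06 and t = 12, the exponentials are 0.3969, 0.3536 and 0.1932. The first quotient is 0.0433/0.00963 = 4.50 and the second is (−0.1604)/(−0.0504) = 3.18. So S(12) ≈ 0.397 + 0.0770 × 1.314 = 0.498, and the median is about 12.0 months. Likewise S(10.3) = 0.501 for μ = 0.03, and S(14.1) = 0.499 for μ = 0.10. The medians are therefore about 10.3, 12.0 and 14.1 months against a true 9.

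**Step 3: milder assumptions (simulation, same true median of 9).**

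| After assessment stops | 3%/month | 6%/month | 10%/month |
|---|---|---|---|
| Death only | 10.3 | 12.0 | about 14 |
| Half of relapses found per 3-monthly contact; new therapy at a median of 2 months after relapse | 9.4 | 9.6 | 10.0 |
| All found at the next contact; same new therapy | 9.2 | 9.5 | 9.7 |

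At 1% per month with detection or new therapy, the median is about 9.1. Other mixes of partial detection and new therapy reach about 11.1 at 10% per month.

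A second simulation assumed a true median to relapse of 6 or 12 months, 1% to 6% per month stopping assessment, and a mean of 2 or 6 months from relapse to new therapy or death. It gave an excess of 0.5% to 16%. The worst cases were 5.6 becoming 6.4 months and 10.4 becoming 12.1 months. At 1% per month the excess was at most about 3%.

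**Step 4: the event mismatch.** Assume 10% per year die or start new therapy without relapse. Hazards add, so the three-event median is 0.693/(0.693/12 + 0.10/12) = 0.693/0.0661 = 10.5 months against 12 for relapse only, and 0.693/(0.693/6 + 0.10/12) = 0.693/0.1239 = 5.6 months against 6. The 7.5.3 event list gives the shorter duration.

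**Step 5: does censoring at the last assessment repair it?** If only event-free subjects are cut back and late events are kept, the median ranges from about 8.1 to 10.4 months against a true 9. Late events stay in while the matching event-free time is dropped. If events first recorded after the lapse are also censored at the last assessment, the median is 8.9 to 9.1 in every scenario, provided stopping assessment is unrelated to relapse risk.

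**The case against.** The case against making much of this is substantial, and most of it stands.

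- Relapse is not defined by blasts alone. Investigator-determined clinical progression counts, SAP Appendix C also accepts clinical or symptomatic progression, and new therapy and death are events. A visit can therefore pick up several events without a marrow. This stands, and it is why the milder rows in the table are more plausible than the top one.
- A reader might infer that follow-up visits involve no disease assessment. The SAP says only that a visit suffices, and the European AML protocol that would describe it is not available. What does stand is that 7.5.3 names the visit as an alternative to marrow or blood assessment, so its own wording requires no blast result.
- Cutting event-free subjects back to the last assessment, on its own, can bias the median downward. This stands (Step 5), and the fix has to deal with late events.
- The leukemia-free survival rule belongs to a different endpoint and population, and SAP 1.0 says that the SAP supersedes the protocol's high-level analysis plan. It shows that the sponsor has used assessment-based censoring, not that 7.5.3 breaches a requirement.
- The endpoint is descriptive, with no formal comparison between sequences (SAP 7.5). With an assumed 30 responders, sampling error alone spans roughly 5.5 to 15.8 months around a median of 9.
- 3.2.2 is an endpoint list and 7.5.3 the working derivation, so a programmer would probably follow 7.5.3. That softens the inconsistency but does not remove it.

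**Conclusion.** Two modest points hold on the current SAP text.

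First, 7.5.3 permits unassessed time to count as remission, so the duration can be overstated. A reader might go further and say that the reported duration is overstated. The documents do not support that: bias needs relapses that are missed or found late after the last assessment, and nothing in them fixes how often that happens. On an assumed true median of 9 months and 1% to 10% per month stopping assessment, about 9.1 to 11.1 months is the range when later relapses are partly detected or lead to new therapy. About 14 months needs 10% per month stopping and nothing but death recorded afterwards.

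Second, 3.2.2 and 7.5.3 define the endpoint differently. A reader might take this as a further cause of overstatement. It works the other way, because the extra events in 7.5.3 shorten the duration relative to relapse only.

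Both deserve correction, but neither touches the primary AUC equivalence analysis.

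**What to change.** In SAP 7.5.3:

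1. Censor event-free responders at the last adequate marrow or blood assessment without relapse, and drop the follow-up visit as a censoring point.
2. State that an event first recorded after assessment has lapsed, for example after two or more missed scheduled assessments, is censored at that last assessment. Define a lapse for subjects off treatment as well, since the supplied protocol schedules no marrow or blood count in follow-up after the discontinuation visit.
3. Keep the current contact-based rule, with all late events counted, as a sensitivity analysis. It also guards against the possibility that stopping assessment is related to relapse risk.
4. Apply the same rules to duration of CR and of CR or CRp.

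In SAP 3.2.2, state the same event list as 7.5.3.

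The cost is SAP wording and one extra Kaplan-Meier table. The primary version will have fewer events and somewhat shorter follow-up, so its intervals will be a little wider. No new data are needed.
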